**11. VCU Health System locations**

1. \* Will research activities occur in patient care areas of the VCU Health System (including at CHoR, Community Memorial Hospital, Tappahannock Hospital, VCU Medical Center and Massey Cancer Center)?

Yes  
 No

2. \* The PI has reviewed and agreed to comply with the VCU Health System Research in Patient Care Areas policy ([https://research.vcu.edu/compliance\\_program/vcuhs\\_policies.htm](https://research.vcu.edu/compliance_program/vcuhs_policies.htm)):

Yes  
 No

**12. VCUHS Department of Pathology**

Learn more about requesting and establishing an account with Pathology here: See <https://pathology.vcu.edu/research-services/>

1. \* I have contacted VCUHS Department of Pathology to determine feasibility if my study involves the following:

- Storage of Microbiology isolates
- New instrumentation provided by clinical trial/study sponsor, or
- Non-routine specimen processing (examples include but aren't limited to the following: addition of reagents to samples/aliquots, buffy coat processing, DNA sample processing)

Yes  
 No  
 N/A - my study does not involve any of the listed processes.

2. \* If my study involves specimen retrieval from the Pathology laboratory, I have established a process with Pathology to deidentify and retrieve specimens.

Yes

No N/A - my study won't involve specimen retrieval from Pathology**13. VCU Institutional Biosafety Committee (IBC)**

To contact the Biosafety Office see their website at: <https://research.vcu.edu/integrity-and-compliance/compliance/regulatory-committees/>

1. \* Does this project involve any of the following hazardous biological agents ("biohazardous agents") that have NOT been FDA approved? These may include, but are not limited to, any of the following. If you are unsure, please contact the Biosafety Office:

- Any functional recombinant viruses (especially viruses that may integrate into the patients' genome).
- Expression or administration of biological toxins.
- Live pathogenic or potentially pathogenic organisms of plants or animals (bacteria, fungi, wild-type viruses, parasites, etc.), that are, or potentially may be, in experimental products.
- Introduction or expression of rDNA or synthetic nucleic acids
- Use of a product (e.g., monoclonal antibodies, recombinant cytokines) produced from virally infected mammalian cells.
- Use of a product (purified growth factors, cytokines) produced from mammals or their cells.

 Yes  No**14. VCU Radiation Safety Committee (RSC)**

To contact the Radiation Safety Section see their website at: <https://research.vcu.edu/integrity-and-compliance/compliance/regulatory-committees/>

1. \* Does this study involve radiation exposure and/or scans involving radiation (e.g.: PET, MRA, CT, DXA, nuclear medicine, etc.)?

 Yes No**15. VCU Scientific Review Committee (SRC)**

For guidance, see <https://cctr.vcu.edu/support/consultation/scientific-review-committee/>

1. \* Has this human subjects protocol (not the grant application) already been reviewed by the funder of a sponsored project (e.g. a federal, state or non-profit funding sponsor)?

 Yes No**16. Upload any documents requested in the questions above:**

Document Name	Document	Version	Date Modified	Uploaded By	Type	Approved
View Consent Form	Consent 11.29.22 Clean.pdf	0.21	12/1/2022 10:30 AM	[name]	Consent/Assent/Information Sheet	Yes
View [name] CV	[name] CV.docx	0.01	10/28/2022 11:45 AM	[name]	CV/Biosketch	Yes
View Research Presentation Script and Flow Sheet	Research Presentation Flow- FINAL.docx	0.04	8/16/2020 6:50 PM	[name]	Research Protocol	Yes

Document Name	Document	Version	Date Modified	Uploaded By	Type	Approved
View Research Consent Presentation and Flow Sheet FINAL.docx	Research Consent Flow Sheet - and Flow Sheet FINAL.docx	0.03	8/16/2020 6:50 PM	[name]	Research Protocol	Yes
View Anesthesia Data Collection as part of Data Collection Packet	Anesthesia flow chart.docx	0.01	7/22/2020 12:04 PM	[name]	Research Measure	Yes
View Data collection packet	Research Data Packet .docx	0.01	7/22/2020 12:02 PM	[name]	Research Measure	Yes
View FDA Lidocaine	Lidocaine - Dental FDA.pdf	0.01	5/13/2020 4:20 PM	[name]	Drug/Device Brochure	Not Applicable
View IND Exemption for Lidocaine	IND Exemption for Lidocaine.docx	0.01	4/17/2020 10:03 AM	[name]	Drug/Device Brochure	Yes
View [name] CV	[name] CV.pdf	0.01	2/18/2020 12:28 PM	[name]	CV/Biosketch	Yes
View GA Post- Op Instructions	General Anesthesia Post-Op Instructions.docx	0.01	12/17/2019 2:00 PM	[name]	Other	Not Applicable
View FLACC Behavior Scale	FLACC Behavior Scale.docx	0.01	12/17/2019 12:03 PM	[name]	Research Measure	Yes
View Parent's Post Operative Pain Measure	Parents Post Operative Pain Measure.docx	0.01	12/17/2019 12:03 PM	[name]	Research Measure	Yes
View MSDS Lidocaine	MSDS.pdf	0.01	12/4/2019 1:14 PM	[name]	Drug/Device Brochure	Not Applicable

# HIPAA

In order for VCUHS to meet HIPAA regulations regarding accounting of disclosures, data retention, and data destruction requirements for PHI data obtained without patient authorization, members of the study team (including principal investigators) are directed to consult with VCU Informatics to obtain any VCUHS data. This does not include obtaining data for which the study team has patient authorization. [VCU Health System Authority and Affiliates Policy COMP-014]

For data requests, including preparatory to research and research with decedents, submit a request for the desired PHI, or for a consultation on alternate methods to obtain the data, at <https://informatics.vcu.edu>.

## HIPAA Privacy Board Requirements

For guidance, see <https://www.vcuhealth.org/our-story/who-we-are/compliance-services/compliance-services>

1. \* Select the source of the Individually Identifiable Health Information. See help text for definitions.

- PHI associated with or derived from (i.e. obtained from or entered into) VCU Health medical records or VCU Dental Care records**
- Research Health Information (RHI) created or received by a study and kept solely in study records (e.g. self reported or the result of research tests and not entered into health records)**
- PHI associated with or derived from (i.e. obtained from or entered into) a non-VCU HIPAA covered entity's health records**

2. \* Summarize the types of health information that will be obtained or used in this research. Do not describe only the identifiers that you will collect or use during the study.

As part of the study patient anesthesia record, and patient dental record will be reviewed and used in this research.

3. \* Describe the source(s) of the protected health information (e.g. Informatics or which clinical databases):  
Patient charts in VCU Cerner and VCU Dental Axium.

4. \* Does the PI certify that this study's access to and use of the protected health information is limited to the minimum amount necessary to be able to effectively conduct the research?

Yes  No

5. \* Select all pathways this research will employ to use or access PHI (selections will branch):

- De-Identified Data (none of the 18 identifiers are recorded or associated with the research data)
- Limited Data Set
- Waiver of Authorization
- Partial Waiver of Authorization (temporary waiver for recruitment purposes and/or waiver of some elements of Authorization)
- Signed Authorization Combined with Consent Form**
- Signed Authorization as Stand-Alone Form

**HM20018316 - [name]**

**The Effect of Local Anesthesia when used in Dental Restorative Cases Under General Anesthesia on Postoperative Comfort**

## Institutional Requirements Complete

Protocol Progress:

- **INITIAL SETUP**
- **BACKGROUND, RATIONALE & GOALS**
- **RESEARCH PLAN**
- **CONSENT PLAN**
- **RISKS, PRIVACY & CONFIDENTIALITY**
- **POPULATIONS WITH SPECIAL CONSIDERATIONS**
- **INSTITUTIONAL REQUIREMENTS**
- ⑧ **DOCUMENTS**

Click Continue below to go to the next section

## Documents

### 1. Upload any documents that the VCU IRB will need to conduct a review of this submission:

A list of potential documents is given in the help text.

**NOTE:** The delete function should only be used if an incorrect document is uploaded or added to the system AND that document has not been reviewed and approved by the IRB. Do NOT delete documents that the IRB previously reviewed and approved.

Once you have uploaded a document to RAMS-IRB, any changes to that document (i.e. different versions of the same document) should be added to the IRB submission by using the Update button. To provide updated documents, follow these steps:

- Click the *Update button located to the left of the document to be updated.*
- In the *Add Document* window, click the *Choose File or Browse* button, select the file you are adding, and click on the *Open* button.
- Click *OK* to close the *Add Document* window, and the system will upload the revised document. RAMS-IRB will automatically provide a version number for the document.

To access previous versions of a document in RAMS-IRB you must use the History link associated with the document.

- Click the *View or Update button located to the left of the document you wish to access.*
- In the *Add/View Document* window, click the *"History"* hyperlink located to the right of the file name.
- A separate window will open that shows all versions of the document that have been added to RAMS-IRB. Click on any file name to download and view the document.

Document Name	Document	Version	Date Modified	Uploaded By	Type	Approved
View Consent Form	Consent 11.29.22 Clean.pdf	0.21	12/1/2022 10:30 AM	[name]	Consent/Assent/Information Sheet	Yes
View [name] CV	[name] CV.docx	0.01	10/28/2022 11:45 AM	[name]	CV/Biosketch	Yes
View Research Presentation Script and Flow Sheet	Research Presentation Script and Flow Flow- FINAL.docx	0.04	8/16/2020 6:50 PM	[name]	Research Protocol	Yes
View Research Consent Presentation	Research Consent Flow Sheet - and Flow Sheet FINAL.docx	0.03	8/16/2020 6:50 PM	[name]	Research Protocol	Yes
View Anesthesia Data Collection as part of Data Collection Packet	Anesthesia flow chart.docx	0.01	7/22/2020 12:04 PM	[name]	Research Measure	Yes
View Data collection packet	Research Data Packet .docx	0.01	7/22/2020 12:02 PM	[name]	Research Measure	Yes
View FDA Lidocaine	Lidocaine - Dental FDA.pdf	0.01	5/13/2020 4:20 PM	[name]	Drug/Device Brochure	Not Applicable
View IND Exemption for Lidocaine	IND Exemption for Lidocaine.docx	0.01	4/17/2020 10:03 AM	[name]	Drug/Device Brochure	Yes
View [name] CV	[name] CV.pdf	0.01	2/18/2020 12:28 PM	[name]	CV/Biosketch	Yes
View GA Post- Op Instructions	General Anesthesia Post-	0.01	12/17/2019 2:00 PM	[name]	Other	Not Applicable

Document Name	Document	Version	Date Modified	Uploaded By	Type	Approved	
	Op Instructions.docx						
View	FLACC Behavior Scale	FLACC Behavior Scale.docx	0.01	12/17/2019 12:03 PM	[name]	Research Measure	Yes
View	Parent's Post Operative Pain Measure	Parents Post Operative Pain Measure.docx	0.01	12/17/2019 12:03 PM	[name]	Research Measure	Yes
View	MSDS Lidocaine	MSDS.pdf	0.01	12/4/2019 1:14 PM	[name]	Drug/Device Brochure	Not Applicable

## Documents Complete

Protocol Progress:

- **INITIAL SETUP**
- **BACKGROUND, RATIONALE & GOALS**
- **RESEARCH PLAN**
- **CONSENT PLAN**
- **RISKS, PRIVACY & CONFIDENTIALITY**
- **POPULATIONS WITH SPECIAL CONSIDERATIONS**
- **INSTITUTIONAL REQUIREMENTS**
- **DOCUMENTS**

End of Application

Click Continue below to exit and submit this project

## Bio-Medical Project Drugs

**1. \* Drug:**

2% Lidocaine with 1:100,000 epinephrine

**2. \* Manufacturer:**

Henry Schein

**3. \* Select all types that apply:** **FDA Approved and being used as approved** Marketed Drug/Biologic Exempt from IND Investigational Drug/Biologic/Supplement used as drug Supplement Over the Counter Medication Other (Drug or Compound Not Listed Above)**4. \* Will the doses of drug administered and the dosing schedule match FDA approved labeling: (if not, include all doses and dosing schedules in the Methods)** Yes No Not Applicable**5. \* Select who holds the Investigational New Drug (IND) application for the drug/biologic:** External to VCU Sponsor or Investigator VCU Sponsor-Investigator VCU Sponsor who is not the Investigator Not Required**6. Indicate the drug's IND number, if applicable. If the drug qualifies for IND exemption, enter "IND Exempt":**  
IND Exempt

## Consent Groups

1. \* Enter a descriptive name for this consent / assent group:

Parent/ Guardian Consent

2. \* Select all that apply to this consent / assent group:

**Name**

Signed Consent by Participant

**Signed Parent/Guardian Permission or Legally Authorized Representative Consent**

Signed Assent by Child or Decisionally Impaired Adult

Verbal/Other Indication of Assent by Child or Decisionally Impaired Adult

**Short Form Consent (limited applicability)**

None of the Above (select waiver below)

3. \* Select all electronic signature platforms that apply to this consent / assent group:

**Not using electronic signature platforms**

DocuSign Part 11 (FDA regulated studies)

DocuSign (standard platform for non-FDA regulated studies)

REDCap e-Consent

iMedConsent (Veterans Affairs studies)

Other electronic signature platform

4. If Other is selected, explain:

5. \* Select any waivers that apply to this consent / assent group:

**No Waivers Requested**

Waiver of All Consent or Some Elements in Consent Form

Waiver of Parental Permission or Legally Authorized Representative Consent

Waiver of All Assent by Child or Decisionally Impaired Adult

Waiver of Signature on Consent/Permission Forms (waiver of documentation of consent)

Exception from Informed Consent (for emergency research only)

6. \* Select all study team role(s) that will obtain consent / assent from this group:

**Principal Investigator**

**Co/Sub-Investigator**

Medical or Psychological Responsible Investigator

**Lead Student/Trainee Investigator (leading their own project)**

Research Coordinator

Research Nurse

Consultant

Research Assistant

Pharmacist

Statistician

Regulatory Coordinator

Trainee/Student(working on project)

Other

N/A: Requesting Waiver of Consent

**7. \* Describe the consent procedures used for this group. Address each point below:**

- When and where consent will occur
- What will be covered during the consent discussion
- How the consent discussion will occur (e.g. in-person, phone, video conference)
- How you will reconfirm consent on an ongoing basis, if applicable

Parents will be initially presented with the option to be considered to participate in the study at the end of their consultation for surgery visit. Parents will be provided with a copy of the consent form on that date. Parents will be asked to sign consent day of surgery preoperatively

**8. \* Select the processes for minimizing any potential perception of undue influence to participate, particularly when there is a pre-existing relationship between the participant and the researcher (e.g. treatment provider/patient; instructor/student; supervisor/employee, etc.):**

- Having a 3rd person (family/friends, another study team member, etc.) present during the consent / assent discussion
- Having an independent advocate (e.g. advocate for decisionally impaired adults, wards) present during the consent / assent discussion
- Removing physical symbols of authority like white coats or police badges
- Sitting down beside the participant instead of standing over them
- If obtaining consent / assent in a clinical setting, letting patients sit instead of lie down (if they are able to)
- Moving to a more neutral location like a conference room
- Obtaining consent / assent after other services/interactions have been completed (e.g. after school or the clinic visit)
- Having a mandatory wait period for the participant to go home and think before they sign consent /assent
- Sharing the consent / assent discussion between two people (i.e. a clinician might be the best person to explain study procedures and risks, but then they could step out and let a research assistant finish the consent process)

**Other protection(s) not listed here – describe below**

N/A: Requesting Waiver of Consent

**9. \* Describe the other ways the study team will minimize any potential perception of undue influence to participate:**

All parents of patients will be given the consent forms at the day of their consultation and be given the opportunity to think about whether they would wish to participate at home with their family. Consent will be performed by a separate nurse day of surgery after consent for dental treatment under general anesthesia by the dental surgery team on that date. Families will be informed that their decision will not alter the dental care that will be rendered whether they choose to proceed or not. To help to minimize coercion we are having a separate nurse obtain consent after all other consents have already been obtained.

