**See the help text for additional guidance**

This study has been modeled as a double-blinded randomized control trial. Patients will include healthy children (ASA 1 or ASA 2) without any history of behavioral issues under the age of 6 who had been treatment planned to have exclusively; restorative work, prefabricated crowns and space maintainers.

Dental treatment will be performed under general anesthesia at the Children's Hospital of Richmond Brook Rd. and Children's Pavilion Campuses. Sixty candidates will be recruited from patients presenting for or needing full mouth dental rehabilitation. Patients will be recruited by doctors from VCU Pediatric Dental Clinic and Children's Hospital of Brook Rd. Pediatric Dental Clinic during GA consultation appointments. Participant information will be collected and enclosed in a Google Doc Sheet on Secure VCU Server. Patients will be assigned a participant number which will be used to randomize participants and de-identify patient information. Patients will be randomized into two groups; those that receive LA while under GA and those that will not.

Day of surgery, patients will be evaluated preoperatively using the FLACC pain/behavior scale by the preoperative nurse who is blinded to the candidates group in the study. Intraoperatively, patients will be given either local anesthetic (2% Lidocaine with 1:100,000 epi) infiltration at six sites (once at each of the 6 sextants, L posterior, anterior, R posterior on each arch) of the mouth by the dental surgeon performing the surgery or no local anesthesia will be utilized. Administration of local anesthetic will be a weight based calculation and will be locally infiltrated 10 minutes prior to the end of the procedure. Postoperatively patients will be evaluated in the Post Anesthesia Care Unit (PACU) by a nurse blinded to the intervention before discharge using the same initial pain/ behavior scale, the FLACC scale, used preoperatively. Patients will then be discharged to home when stable and parents of patients will then be given a standard set of post-operative instructions encompassing instructions for the possibility of anesthetized tissues (see documents). Patient's time in the PACU will be noted upon discharge. Lastly, that evening parents were asked to evaluate their children over the phone using a parent administered post- operative evaluation, the Parent's Post-Operative Pain Measure (PPPM).

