**See the help text for additional guidance**

As part of the study patients will be assigned local anesthetic protocol based upon treatment group. Local anesthesia use in dental cases under general anesthesia varies greatly from provider to provider. Ordinarily provider preference would dictate use. No alteration will be made to local anesthesia routine use. Standard infiltration volumes will be used in this study and will be administered based on a weight-based calculation. Location of local anesthetic will be infiltrated in all 6 sextants of the oral cavity. No additional medical tests will be performed as part of the study. As part of the study patients will have a pre- and post operative FLACC score pain assessment. This is a standard pain assessment that is routinely preformed by nursing staff regardless of participation in the study upon patient arrival and before patient departure. Next, throughout the study the patient will be observed by the anesthesiologist throughout the procedure as customary and the anesthesiologist will intervene as customary by deepening the anesthetics if needed. As part of the research patients will be contacted by postoperative phone call which is customary, however as part of this phone call parents will be asked questions to assess patients post operative pain using the parents post operative pain measure tool which is not customary and data will be solely collected for research.

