**Study specific activities:**

1. Randomization to LA

2. Recording FLACC score pre/postop, time in PACU
3. Parent/guardian pain measure tool during standard postop phone call

**8. If applicable, describe alternatives (research or non-research) that are available to potential participants if they choose not to participate in this study:**

If patients do not choose to participate in this study they will undergo FMDR under GA with LA as prescribed by the dentist and anesthesiologist providing the case.

**9. Upload any supporting tables or documents (e.g. protocol documents, figures/tables, data collection forms, study communications/reminders):**

**Upload ALL instruments/guides that will be used or that participants will experience (i.e. see, hear, complete), including measures, scripts/questions to guide interviews, surveys, questionnaires, observational guides, etc.:**

**Upload ALL recruitment and screening materials, including such as ads, flyers, telephone or in-person scripts, letters, email invitations, TelegRAM announcements, and postcard reminders, screening scripts, screening forms, and screening measures:**

Document Name	Document	Version	Date Modified	Uploaded By	Type	Approved
View Consent Form	Consent 11.29.22 Clean.pdf	0.21	12/1/2022 10:30 AM	[name]	Consent/Assent/Information Sheet	Yes
View [name] CV	[name] CV.docx	0.01	10/28/2022 11:45 AM	[name]	CV/Biosketch	Yes
View Research Presentation Script and Flow Sheet	Research Presentation Script and Flow Flow- FINAL.docx	0.04	8/16/2020 6:50 PM	[name]	Research Protocol	Yes
View Research Consent Presentation	Research Consent Flow Sheet - and Flow Sheet FINAL.docx	0.03	8/16/2020 6:50 PM	[name]	Research Protocol	Yes
View Anesthesia Data Collection as part of Data Collection Packet	Anesthesia flow chart.docx	0.01	7/22/2020 12:04 PM	[name]	Research Measure	Yes
View Data collection packet	Research Data Packet .docx	0.01	7/22/2020 12:02 PM	[name]	Research Measure	Yes
View FDA Lidocaine	Lidocaine - Dental FDA.pdf	0.01	5/13/2020 4:20 PM	[name]	Drug/Device Brochure	Not Applicable
View IND Exemption for Lidocaine	IND Exemption for Lidocaine.docx	0.01	4/17/2020 10:03 AM	[name]	Drug/Device Brochure	Yes
View [name] CV	[name] CV.pdf	0.01	2/18/2020 12:28 PM	[name]	CV/Biosketch	Yes

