## Risks, Discomforts, Potential Harms and Monitoring

1. \* **Describe the risks of each research procedure to participants or others. For each identified risk, provide an assessment of the anticipated seriousness and likelihood of the risk. Some examples of possible risks include but are not limited to:**

- **Physical risks (e.g. bodily harms or discomforts, side effects, etc.)**
- **Psychological risks (e.g. emotional, mental, or spiritual harms or discomforts, changes to thoughts, beliefs, or behaviors, etc.)**
- **Research data risks (e.g. loss of confidentiality and privacy)**
- **Social or legal risks (e.g. impacts on relationships or reputation, legal or criminal justice actions for self or others, etc.)**
- **Financial risks (e.g. impacts on income, employability, or insurability, loss of services, etc.)**
- **Other risks (e.g. unforeseeable risks of experimental procedures, risks related to particular study designs (randomization, washout, placebo, withholding care/services, deception), etc.)**

See the help text for additional guidance.

Local anesthesia is routinely used in dental treatment and can lead to short term post operative numbness. In patients that will receive local anesthesia they will have transient numbness that can lead to some discomfort due to the temporary altered sensation in the area. Additionally due to the numb sensation some patients can cause inadvertent self inflicted trauma in the area. Additionally, throughout the course of this study there is a risk of loss of confidentiality thorough lost or shared information. Last, anticipate the risk of survey completion that being asked survey questions may cause distress or anxiety since their child will be evaluated. In addition, as part of a randomized control trial groups will be randomized using block randomization- participants will not be able to choose their protocol once enrolled in the study.

2. \* **Describe how each of the risks/harms/discomforts identified above will be minimized:**

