After a patient has been accepted in the study and consent obtained patients will only be withdrawn if it is determined during comprehensive exam under GA if a patient requires EXT of any teeth. In that case patient will have local anesthesia administered in the area of extraction, extraction will be performed and patient will be withdrawn from the study. Patients given Precedex or Ketolorac post-operatively by the anesthesiologist will be withdrawn from the study. These are given based on anesthesia provider's preference. The protocol will discourage the use of these medications for study participants as it would alter the effects of the intervention.

6. \* **Summarize any pre-specified criteria that would trigger the investigator/sponsor/monitoring committee to stop or change the study protocol due to safety concerns:**

None anticipated. Study is evaluating methods that are currently utilized to evaluate which has better patient response. No safety concerns anticipated as lidocaine 2% with 1:100,000 epi is routinely used by some providers in FMDR under GA.

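### Families are to be told that their decision does not alter the dental care given, which is inaccurate as written: enrolment replaces the provider's decision on local anesthesia with randomization

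*Combined protocol and SAP*

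**What the plan says.** The assurance is in the combined protocol, Consent Groups, item 9, which asks how perceived undue influence will be minimized: "Families will be informed that their decision will not alter the dental care that will be rendered whether they choose to proceed or not".

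Other sections describe what happens to the child under each choice:

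- **Family declines.** Study Procedures, item 8 (alternatives): "they will undergo FMDR under GA with LA as prescribed by the dentist and anesthesiologist providing the case". Item 7 of the same section gives the usual rule: "Ordinarily provider preference would dictate use".
- **Family enrols.** Study Procedures, item 6: "Patients will be randomized into two groups; those that receive LA while under GA and those that will not". Item 7: "As part of the study patients will be assigned local anesthetic protocol based upon treatment group". The risk section (Risks, Discomforts, Potential Harms and Monitoring, item 1) adds that "participants will not be able to choose their protocol once enrolled in the study".
- **A second assurance.** Study Procedures, item 7, also states: "No alteration will be made to local anesthesia routine use".
- **Two post-operative drugs.** Item 5 of the risk section says of Precedex and Ketorolac: "The protocol will discourage the use of these medications for study participants as it would alter the effects of the intervention". The exclusion criteria (Study Population, item 5) put this as a recommendation to the anesthesiologist and describe the drugs as not standard of care.

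**The concern.** The assurance covers both choices and speaks of the care itself. It does not speak of access to care, of its quality, or of freedom from penalty. Local anesthetic given by the dental surgeon is part of dental care, and it is the one element of care that the trial assigns. The sentence therefore denies a change in the thing that the randomization controls.

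The children are under 6 and no assent is taken (Children, item 4), so parental permission is the only safeguard of choice. The risk section names numbness, self-inflicted trauma in the numb area and loss of choice of group as consequences of taking part. A parent told that care is the same either way may be misled when weighing these. If the consent form explains randomization properly, the parent receives two messages that disagree.

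**Working it through.** The plan gives no figure on this point, so there is none to reproduce. The check has two parts.

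**1. The statements side by side**

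| Question | Declines | Enrols |
|---|---|---|
| Who or what decides on local anesthetic? | Dentist and anesthesiologist (Study Procedures, items 7 and 8) | Randomized group (Study Procedures, items 6 and 7) |
| Can the family choose the group? | Not applicable | No (risk section, item 1) |
| Site and timing of any injection | Not set by the study | Six sites, 10 minutes before the end of the procedure (Study Procedures, item 6) |
| Precedex or Ketorolac after surgery | Anesthesia provider's preference (risk section, item 5) | Discouraged, with withdrawal from the study if given |

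The first row alone contradicts the assurance. It also contradicts the second assurance, in Study Procedures, item 7, which stands beside the statement that group determines local anesthetic use.

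**2. How many children receive a different yes/no decision**

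Inputs:

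- Maximum enrolment N = 60 (Study Population, item 2).
- r = share randomized to local anesthetic. The risk section says block randomization but gives no ratio, so 1:1 is an assumption, varied below.
- p = share of enrolled children whose own provider would have given local anesthetic. It is not known for these sites, so the full range 0 to 1 is used. The survey cited in the Background section reports 21% of dentists who never use it in such cases and 8% who always do.

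The decision differs when a child is randomized to local anesthetic but would not have had it, or the reverse:

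share changed = r(1 − p) + (1 − r)p

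- 1:1, r = 1/2: 0.5(1 − p) + 0.5p = 0.5 for any p. Expected number: 0.5 × 60 = 30 changed, 30 unchanged.
- 1:2, r = 1/3: 1/3 + p/3, which runs from 33% (20 of 60) at p = 0 to 67% (40 of 60) at p = 1.
- 2:1, r = 2/3: 2/3 − p/3, which runs from 67% (40 of 60) at p = 0 to 33% (20 of 60) at p = 1.

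A stricter count treats every study injection as a change, because its sites and timing are fixed by protocol:

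share changed = r + (1 − r)p

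At 1:1 this is 50% at p = 0, 75% at p = 0.5 (15 of 60 unchanged) and 100% only at p = 1. It reaches every enrolled child only if every provider would always have given local anesthetic.

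**The case against.** The strongest reply is context. The sentence answers a question about undue influence and is followed by one about minimizing coercion. The natural intention is that treatment does not depend on joining. That is very likely what was meant, but the words promise that the care is the same, and in this trial it may not be.

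A second reply is that parents do not rely on this sentence alone. They receive the consent form at the consultation, can take it home, and sign on the day of surgery. The nurse works from a script and flow sheet. None of those texts is in the documents, and the risk section shows that the team recognizes the loss of choice. This stands against any claim that parents cannot weigh what the trial changes. It does not remove the conflict.

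Some stronger readings are tempting, and the documents do not support them:

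- *The statement is false for every family.* Families who decline also hear it and keep usual care. Under 1:1 allocation an expected half of enrolled children get the yes/no decision that their provider would have made.
- *The two drugs prove the point by themselves.* They are the anesthesiologist's choice, so it is arguable whether they are dental care at all. The measure is a recommendation and not a ban, although a child who receives either drug is withdrawn. They are secondary support.
- *Families who feel misled will refuse the evening telephone pain assessment.* Nothing in the documents bears on this.

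It can also be said that the second assurance, in Study Procedures, item 7, refers only to technique and volumes, since the next sentence there concerns standard volumes. That is possible, but the words refer to use, and use is what the group assignment sets.

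**Conclusion.** The concern holds as a conflict between what families are to be told and what the design does. For every enrolled child, the decision on local anesthesia passes from the provider to chance. For an expected 50% (30 of 60) the yes/no decision itself differs from the provider's, if allocation is 1:1. If it is 1:2 or 2:1 the expected share lies between 33% and 67%. The 1:1 result does not depend on the usual rate of use. It does depend on the ratio, which the protocol does not state.

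The conclusion goes no further than that. Without the consent form and script, it cannot be said that any family is left uninformed, only that this assurance is inaccurate as written and may mislead. It does not affect the validity of the comparison between groups. It should be corrected because it concerns the only permission given for young children and costs almost nothing to put right. No view is taken on when local anesthetic or either of the two drugs should be used.

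**What to change.** 1. In Consent Groups, item 9, replace the sentence with one that keeps the non-penalty assurance and agrees with the design. For example: declining will not affect the child's access to dental treatment or its quality; taking part means that chance, and not the provider, decides whether local anesthetic is given.
2. Check the nurse's script, the flow sheet and the consent form for a matching line and change it in the same way.
3. In Study Procedures, item 7, reconcile the statement that routine use is unaltered with assignment by group. If it was meant to cover only technique or volume, say so.
4. As a secondary point, tell families that the anesthesiologist is asked to avoid two named post-operative drugs in study participants, in line with Study Population, item 5, and the risk section, item 5.

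The cost is a minor amendment covering two protocol passages and any matching script or consent text. A few more families may decline once the statement is accurate. No clinical rule, randomization procedure or outcome changes.
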